5.4. Duration of Follow-Up

The subjects will begin follow-up care and the time of initial discharge after transplant and continue for up to 5 years from date of stem cell transplant or until death or patient withdrawal.

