5.5.3.4. Pregnancy

5.5.4. Treatment Plan

5.5.4.1. Stem Cell collection and cryopreservation of peripheral blood stem cells

5.5.4.1.1. The patient will undergo a collection of adequate numbers of hematopoietic stem cells. Stem cell harvesting may be done after priming with a cytokine (G-CSF, GM-CSF or other factors used singly or in combination according to institutional preference) or they may be collected following the salvage chemotherapy during the rebound phase with cytokine support. Chemotherapy in combination with growth factors is also allowed.

5.5.4.1.2. Stem cells should be collected no longer than six weeks after completion of last cycle of salvage chemotherapy. The patient will undergo leukapheresis according to standard institutional procedures to collect a minimum of $4 \times 10^6/\text{kg}$ CD34+ cells desired. Separate institutional informed consent forms will be used.

5.5.4.1.3. The collected cells must be cryopreserved according to accepted methods using DMSO alone or DMSO/HES. The stem cells should not be purged or CD34 selected. The collected stem cells will be reinfused after conditioning chemotherapy.

5.5.4.1.4. Patients who fail to collect adequate CD34 cells will be excluded from the study.

5.5.4.1.5. Stem cells will be thawed and infused according to standard institutional practices on Day 0.

5.5.4.1.6. Patient may receive premedication with diphenhydramine, mannitol, hydrocortisone and acetaminophen per institutional protocol.

5.5.4.2. All patients transplanted per the PEDIATRIC BMT SERVICE will have chemotherapy dosed on actual body weight. If the patient's weight is more than 130% of their ideal body weight, then calculate the doses of chemotherapy according to the adjusted ideal body weight using the following formula:

Adjusted ideal body weight = ideal body weight + [(total body weight-ideal body weight) x 0.25].

5.5.4.2. Dose modifications may occur as clinically indicated, at the discretion of the treating physician.

5.5.4.3. Mesna shall be started prior to initiation of Ifosfamide administration per institutional standard. Other measures of uroprotection, such as hydration and furosemide shall be carried out per institutional standard and at the discretion of the treating physician.

5.5.4.4. Renal function shall be monitored as per institutional standard and Carboplatin dose adjusted if clinically indicated.

| DAYS BEFORE TRANSPLANT | | | | | | |
|--|---------|-------|-------|-------|---------|-------|

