| Treatment | Day - 5 | Day-4 | Day-3 | Day-2 | Day - 1 | Day 0 |
| Ifosfamide (2.5 g/m ² /day) IV over 17 hours for four days | X | X | X | X | | |
| Carboplatin (300 mg/m ² /day) IV over 3 hours for four days | X | X | X | X | | |
| Etoposide (300mg/m ² /day) IV over 3 hours for four days | X | X | X | X | | |
| Stem Cell Infusion (Minimum 48 of hours from last dose). | | | | | | X |

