5.5.6. Possible Risks

- 5.5.6.1.** Aggressive supportive care improves outcome. This study will follow the institutional supportive care guidelines for high-dose chemotherapy and stem cell transplant.
- 5.5.6.2.** The possible risks of this treatment include those associated with high-dose chemotherapy and autologous stem cell transplantation including:

1. Pancytopenia requiring transfusion support
2. Bacterial infection
3. Fungal infection
4. Nausea, vomiting
5. Loss of appetite
6. Mucositis
7. Alopecia
8. Allergic reactions to the chemotherapy agents or supportive care agents
9. Liver damage
10. Kidney damage
11. Hemorrhagic cystitis
12. Sinusoidal obstruction syndrome (SOS) of the liver
13. Engraftment syndrome
14. DMSO adverse effects during stem cell infusion

5.5.6.3. Drug specific risks are listed below:

Possible Side Effects of Carboplatin and Etoposide (Table Version Date: October 8, 2013)

COMMON, SOME MAY BE SERIOUS

In 100 people receiving Carboplatin, Etoposide, more than 20 and up to 100 may have:

- Hair loss
- Vomiting, nausea, diarrhea, loss of appetite
- Infection, especially when white blood cell count is low

COMMON, SOME MAY BE SERIOUS

In 100 people receiving Carboplatin, Etoposide, more than 20 and up to 100 may have:

- Anemia which may require blood transfusions
- Bruising, bleeding
- Belly pain
- Sores in mouth which may cause difficulty swallowing
- Tiredness
- Fever, chills

OCCASIONAL, SOME MAY BE SERIOUS

In 100 people receiving Carboplatin, Etoposide, from 4 to 20 may have:

- Constipation
- Numbness and tingling in fingers and toes
- Allergic reaction which may cause rash, low blood pressure, wheezing, shortness of breath, swelling of the face or throat
- Heart failure or heart attack which may cause chest pain, shortness of breath, swelling of ankles, and tiredness
- Severe skin rash with blisters and peeling which can involve inside of mouth and other parts of the body
- Liver damage which may cause yellowing of eyes and skin, swelling

RARE, AND SERIOUS

In 100 people receiving Carboplatin, Etoposide, 3 or fewer may have:

- Changes in vision
- Changes in taste
- Damage to organs which may cause hearing and balance problems
- Cancer of bone marrow (leukemia) caused by chemotherapy

Possible Side Effects of Filgrastim (Table Version Date: October 24, 2013)**COMMON, SOME MAY BE SERIOUS**

In 100 people receiving Filgrastim, more than 20 and up to 100 may have:

- Nausea, vomiting
- Pain in bone

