OCCASIONAL, SOME MAY BE SERIOUS

In 100 people receiving Filgrastim, from 4 to 20 may have:

- Anemia which may cause tiredness, or may require transfusion
- Damage to the lungs which may cause shortness of breath
- Internal bleeding which may cause coughing up blood
- Swelling or tenderness of vessels

RARE, AND SERIOUS

In 100 people receiving Filgrastim, 3 or fewer may have:

RARE, AND SERIOUS

In 100 people receiving Filgrastim, 3 or fewer may have:

- Rupture of the spleen leading to bleeding in the belly

Possible Side Effects of Ifosfamide (Table Version Date: May 28, 2013)**COMMON, SOME MAY BE SERIOUS**

In 100 people receiving Ifosfamide, more than 20 and up to 100 may have:

- Anemia which may require transfusion
- Nausea, vomiting
- Infection, especially when white blood cell count is low
- Blood in urine
- Hair loss

OCCASIONAL, SOME MAY BE SERIOUS

In 100 people receiving Ifosfamide, from 4 to 20 may have:

- Abnormal heartbeat
- Bruising, bleeding
- Kidney damage which may cause swelling, may require dialysis
- Fluid around lungs
- Confusion, sleepiness, disorientation
- Sterility

RARE, AND SERIOUS

In 100 people receiving Ifosfamide, 3 or fewer may have:

- Damage to the heart or heart failure which may cause tiredness, shortness of breath, or swelling of ankles

Possible Side Effects of Mesna (Table Version Date: May 28, 2013)**COMMON, SOME MAY BE SERIOUS**

In 100 people receiving Mesna, more than 20 and up to 100 may have:

- Nausea, vomiting
- Tiredness, headache
- Pain in arms, legs
- Unpleasant taste

OCCASIONAL, SOME MAY BE SERIOUS

In 100 people receiving Mesna, from 4 to 20 may have:

- Low blood pressure which may cause feeling faint

RARE, AND SERIOUS

In 100 people receiving Mesna, 3 or fewer may have:

- None

Possible Side Effects related to blood stem cell harvest and infusion

COMMON, SOME MAY BE SERIOUS

In 100 people receiving Ifosfamide, more than 20 and up to 100 may have:

- Nausea and vomiting
- Unpleasant taste and smell of agent used to preserve stem cells when frozen
- Headache
- Fever
- Discolored urine
- Tingling of the lips
- Muscle cramping

OCCASIONAL, SOME MAY BE SERIOUS

In 100 people receiving Ifosfamide, from 4 to 20 may have:

- Seizures (rare)
- Blood loss
- Infection
- Skin rash, hives
- Flushing (redness and warmth of the skin)
- Dizziness or fainting
- Chills
- Changes in heart rhythm (rare and easily treated)

RARE, AND SERIOUS

In 100 people receiving Ifosfamide, 3 or fewer may have:

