8. STUDY ASSESSMENTS AND PROCEDURES

| | Baseline | Day -5 to +14 or Discharge (Daily unless stated otherwise) | After Discharge: Weekly until stable | Day 30 | Day 100 | Every 3 – 6 months | 1 Year | Yearly until 5 years from transplant |
|---|----------|--|--------------------------------------|--------|---------|------------------------------|--------|--------------------------------------|
| H&P with VSS | X | X | X | X | X | X | X | X |
| Performance Status | X | X | X | X | X | X | X | X |
| AE Assess | | X | X | X | X | X | | |
| ECG, ECHO, and/or MUGA Scan, and/or Cardiac MRI | X | | | | | | X | yearly if abnormal |
| PFT's | X | | | | | | X | yearly if abnormal |
| CBC & Diff | X | X | X | X | X | X | X | X |
| PT/PTT/INR | X | | | | | | | |
| BMP, Mg, Phos | X | X | X | X | X | X | X | X |
| LFT's, LDH | X | Weekly | X | X | X | | X | X |
| TFT's (TSH, free T4) | X | | | | | | X | X |
| IgG | X | | | X | X | | X | |
| CD4, CD8 | | | | X | X | | X | |
| CT or MRI Primary / Metastatic Site | X | | | | X | X (at 6 months and 9 months) | X | X |
| PET Scan | X | | | | X | X (at 6 and 9 months) | X | X |

| | | | | | | | | |
|-----------------------------|---|--|--|--|--|--|---|--|
| Audiogram | X | | | | | | X | |
| Creatinine Clearance or GFR | X | | | | | | | |
| DEXA Scan | | | | | | | X | |

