12.6 SAE Reporting: All grade 3 non-hematologic SAE's must be collected, including those thought to be associated with protocol-specified procedures. Collection of all SAEs must continue for 60 days after the last administration of the investigational products. All SAE's must be reported to UF-IRB-01 within 5 working days.

12.7 Laboratory Test Abnormalities – all laboratory test results captured as part of the study should be recorded following institutional procedures. In general, non-clinically significant laboratory deviations are not considered adverse events. Laboratory deviations which require treatment delay, modification or discontinuation or are otherwise clinically significant should be reported as adverse events.

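### Serious adverse event collection is required only to about Day +58 to +60 with no clause for later related events; this conflicts with the visit schedule and leaves late toxicity without a clear route into the safety analysis

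*Combined protocol and SAP*

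**What the plan says.** **Collection and reporting.** Section 12.6: "Collection of all SAEs must continue for 60 days after the last administration of the investigational products". The next sentence reads "All SAE's must be reported to UF-IRB-01 within 5 working days" and carries no end date. Section 12.5 asks for each event to be classed as Related or Not Related, but 12.6 makes no use of that class after day 60.

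**Analysis.** Section 15.4 has patients assessed for adverse events from treatment start to 60 days after the last dose. It then excludes from the safety analysis any event more than 30 days after the last dose.

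**Schedule.** The adverse event row in section 8 reads "AE Assess | | X | X | X | X | X". Against the column headings, it is blank at baseline. It is marked for the inpatient period, the weekly visits, Day 30, Day 100 and every 3-6 months, and the last two columns (1 year; yearly to year 5) are blank. Section 5.4 has follow-up "continue for up to 5 years from date of stem cell transplant or until death or patient withdrawal".

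**Named risks.** Section 5.5.6 lists "Cancer of bone marrow (leukemia) caused by chemotherapy" for carboplatin and etoposide, and "Kidney damage which may cause swelling, may require dialysis" for ifosfamide.

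**Oversight.** Section 13 has all adverse events evaluated for causality and passed to oversight bodies as required, and has the Data and Safety Monitoring Committee review all SAEs. It sets no time limit.

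**The concern.** Aim 3.2 is to evaluate the toxicity of this conditioning regimen. The only stated SAE collection period ends well before the Day 100 visit, and the rules on either side of that date disagree. A site that finds renal failure at Day 100 has a schedule telling it to assess adverse events, a reporting section whose required period has passed, and an analysis section that would exclude the event. At 1 year and yearly, a history and physical, blood count and metabolic panel are all scheduled. Cardiac tests, lung function, thyroid tests, audiogram and DEXA are also due at 1 year. The plan therefore looks for late organ damage at visits where no adverse event assessment is marked.

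With 10 patients, one late toxic event is 10% of the sample. If it is not collected, or is collected and then dropped, the toxicity summary changes materially.

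**Working it through.** **Inputs**

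- Last chemotherapy day: Day -2, from the conditioning table in 5.5.4 ("Ifosfamide (2.5 g/m ² /day) IV over 17 hours for four days | X | X | X | X", under Day -5 to Day -2).
- Stem cell infusion: "Stem cells will be thawed and infused according to standard institutional practices on Day 0" (5.5.4.1.5).
- Required SAE collection and adverse event assessment: 60 days after the last administration (12.6, 15.4).
- Safety analysis cut-off: 30 days after the last dose (15.4).
- Follow-up: up to 5 years from transplant, 5 × 365.25 = 1,826 days.

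The plan does not convert its 60 days into a transplant day, and the sample size of 10 rests on availability, so there is no computed figure to reproduce.

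**Step 1: when the periods close.** Closing day = day of last administration + length of period. The documents do not say which administration starts the clock, so three readings are shown.

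| Clock starts | 30-day cut-off | 60-day period ends | Gap to Day 100 | Share of 5 years |
|---|---|---|---|---|
| Day -2 (last chemotherapy day) | -2 + 30 = Day +28 | -2 + 60 = Day +58 | 100 - 58 = 42 days | 58/1,826 = 3.2% |
| Day -1 (if the 17-hour infusion ends then) | Day +29 | Day +59 | 41 days | 59/1,826 = 3.2% |
| Day 0 (stem cell infusion) | Day +30 | Day +60 | 40 days | 60/1,826 = 3.3% |

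The choice of reading moves the result by two days and does not affect the conclusion.

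**Step 2: the sections side by side.** The 3-6 month column is read as the first year, because it sits between Day 100 and 1 year and its imaging entries are at 6 and 9 months.

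| Period | 12.6: SAE collection required | 15.4: assessed | 15.4: analysed | Section 8: AE row |
|---|---|---|---|---|
| To about Day +28 to +30 | yes | yes | yes | marked |
| Then to about Day +58 to +60 | yes | yes | excluded | marked (weekly until stable) |
| Day 100 and 3-6 monthly visits | not stated | no | excluded | marked |
| 1 year, then yearly to year 5 | not stated | no | excluded | blank |

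The third row is a contradiction between section 8 and sections 12.6 and 15.4. The fourth is a gap: no section calls for adverse event assessment there.

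**Step 3: deaths.** PFS (15.2) counts death from any cause as an event, and OS (15.3) records the date of death from any cause. Imaging is scheduled at Day 100. Whether a patient died without documented progression can therefore be derived. Neither endpoint asks for a cause or an attribution to treatment, and after day 60 no section expressly requires the death to be collected as an SAE.

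**The case against.** The strongest objection is that the 60-day sentence sets a required period and does not order collection to stop. The 5-working-day sentence and section 13 have no end date, and section 8 does look for adverse events at Day 100 and every 3-6 months. This stands in part. It means that a late event is not barred from reaching the IRB or the committee. It does not supply a duty to collect: those passages govern events already recorded, and 15.4 uses the same 60 days as the end of assessment. Section 12.2 shows that the authors wrote an open-ended duty where they wanted one, since pregnancies are followed to outcome. No such wording covers late related SAEs.

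A second objection is that section 13 adopts the cancer center's own monitoring plan, which may cover late events. That plan is not part of the documents. If it does, the protocol should say so.

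Several stronger readings are tempting but not supported:

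- A reader might infer that the committee would see no late SAE. Section 13 is not limited in time, so this does not follow.
- A reader might infer that non-relapse mortality at Day 100 cannot be reported. It can be derived from the PFS and OS data (step 3); what is not required is the cause.
- A reader might apply the risk-table bands to 10 patients to size the loss. Those bands describe whether an event ever occurs. The documents give no onset times, so the share falling after day 60 is unknown. The kidney band is also not a dialysis rate.
- A reader might say that treatment-related death is a named risk. It is not in the risk lists; leukaemia and kidney damage are.

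Finally, a fixed SAE window is a legitimate design choice. That is so, but here the choice conflicts with the protocol's own schedule and provides nothing for related events after it closes.

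**Conclusion.** The point holds as an inconsistency and a gap, not as proof that late events would go unseen. Required SAE collection ends 40 to 42 days before the Day 100 visit, about 3% of the way through a 5-year follow-up, with no clause for later related events. From then to 1 year, section 8 disagrees with 12.6 and 15.4. From the 1-year visit on, no adverse event assessment is marked. An event found late may or may not be collected, and under 15.4 it would be left out of the safety analysis for Aim 3.2.

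The share of calendar time is not a share of events, and no rate of missed events can be derived from the documents. The conclusion assumes that the 60 days in 12.6 is meant as the end of required collection, which 15.4 supports, and that the monitoring plan cited in section 13 does not already cover late related events. The defect does not undermine the trial, but it bears directly on one of its two aims and is cheap to correct.

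**What to change.** Reconcile sections 8, 12.6 and 15.4:

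- **12.6.** State which administration starts the 60-day clock. Add that, after day 60 and through the end of follow-up, three kinds of event are collected: every SAE judged Related under 12.5, every second malignancy, and every death without prior progression, with its cause. Report each to the IRB and the Data and Safety Monitoring Committee within the existing 5 working days.
- **Section 8.** Mark adverse event assessment, limited to these events, at the 1-year and yearly visits. State what the Day 100 and 3-6 month marks cover.
- **15.4.** Extend the assessment period for these events, exempt them from the 30-day exclusion and tabulate them separately. Report non-relapse mortality at Day 100 and 1 year, with causes.

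The 15.4 change is essential: without it, late related events would be collected and then dropped from the analysis. The cost is an amendment to the wording and a few extra forms in 10 patients. No visit is added, because every visit needed is already in section 8, and no treatment rule changes.

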13. DATA SAFETY MONITORING PLAN

This protocol will adhere to the policies of the UF Health Shands Cancer Center Data and Safety Monitoring Plan, in accordance with NCI regulations. The Data and Safety Monitoring Committee will review all serious adverse events and toxicity reports as well as annual reviews. The investigator will continuously monitor the progress of the study and the safety of the participants. All adverse events will be evaluated for causality and reported to the appropriate oversight committees as required.

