The use of high dose chemotherapy followed by autologous peripheral blood stem cell (PBSC) transplantation in recurrent NPC has shown promise when compared with standard chemotherapy. Airoldi and colleagues⁵ reported long-term results of high dose chemotherapy as late intensification with autologous PBSC support in 6 patients. After conventional chemotherapy, there was 1 CR (16%), 3 PR (50%), and 2 NC (34%). After high dose chemotherapy, 4 patients achieved CR (66%), 1 PR (17%), and 1 MR (17%). Toxicity was manageable. After a median follow-up of 30 months (range, 14-50), two

patients were alive without disease (34%), one was alive with bone disease (16%), and three (50%) died of disease at 16, 18, and 24 months⁵.

Chen T-Y et al also reported that high dose chemotherapy followed by autologous stem cell transplantation is feasible with acceptable toxicity and can convert partial remission into complete remission⁶.

3. SPECIFIC AIMS:

- 3.1.** To evaluate the response rates for patients undergoing high dose conditioning using Etoposide, Carboplatin and Ifosfamide followed by autologous stem cell transplantation for the treatment of recurrent NPC in children, adolescents, and young adults.
- 3.2.** To evaluate the toxicities associated with undergoing high dose conditioning using Etoposide, Carboplatin and Ifosfamide followed by autologous stem cell transplantation for the treatment of recurrent NPC in children, adolescents, and young adults.

4. RESEARCH PLAN:

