5.2. Number of Patients Planned

A total of 10 patients are planned to be included in this study.

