12. ADVERSE EVENT REPORTING

12.1. An adverse event (AE) is defined as any new untoward medical occurrence or worsening of a pre-existing medical condition in a patient or clinical investigation subject administered an investigational (medicinal) product and that does not necessarily have a causal relationship with this treatment. An AE can therefore be any unfavorable and unintended sign (including an abnormal laboratory finding) symptom, or disease temporally associated with the use of the investigational product, whether or not considered related to the investigational product.

12.2. *Serious Adverse Events* – any untoward medical occurrence that at any dose:

- Results in death
- Is life-threatening (defined as an event in which the subject was at risk of death at the time of the event; it does not refer to an event which hypothetically might have caused death if it were more severe)
- Requires inpatient hospitalization or causes prolongation of existing hospitalization
- Results in persistent or significantly disability/incapacity
- Is a congenital anomaly/birth defect
- Is an important medical event, defined as a medical event that may not be immediately life threatening or result in death or hospitalization but, based on appropriate medical and scientific judgment, may jeopardize the subject or may require intervention (eg. medical, surgical) to prevent one of the other serious outcomes listed above.
- All pregnancies, regardless of outcome must be reported including pregnancies that occur in the female partner of a male subject. All pregnancies must be followed to outcome.

12.3. *Non-serious Adverse Events* –all adverse events that are not classified as SAE's.

12.4. All adverse events, including those that are serious will be graded according to the National Cancer Institute Common Terminology Criteria for Adverse Events (NCICTCAE, Version 4.0).

12.5. The following categories and definitions of causal relationship to investigational product as determined by a physician should be used:

- 1 **Related** – there is a reasonable causal relationship to the investigational product administration and the adverse event.

2 **Not Related** – there is not a reasonable causal relationship to investigational product administration and the adverse event.

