15.1 Sample Size Determination

This is a pilot study and due to the limited number of potential patients who may present with this rare disease, a sample size of 10 patients was chosen based on availability.

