15.2 Analysis of the Primary Endpoint

PFS is defined as the time from treatment start to the first of either (1) documented disease progression or (2) death as a result of any cause. Patients who did not progress nor die or are lost to follow-up will be censored at the day of their last objective tumor assessment. The Kaplan-Meier method will be used to estimate the median PFS time, together with a 95% confidence interval (CI). PFS will be determined by MRI imaging.

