15.3 Analysis of Secondary Endpoints

The objective RR is equal to the proportion of patients achieving a best overall response of partial or complete response (CR + PR), according to imaging from the start of the treatment until disease progression/recurrence. Clinical benefit rate is equal to the objective RR plus the proportion of patients attaining stable disease (CR + PR + SD). Patients who do not have a tumor response assessment for any reason will be considered nonresponders and will be included in the denominator when calculating the response rate. The number of patients achieving a response will be divided by the total of patients treated to yield the proportion responding. Exact confidence bounds (95% CI) will be calculated.

Overall survival is defined as the time from the date of treatment start to the date of death from any cause. If the patient is alive at the end of the follow-up period or is lost to follow-up, OS will be censored on the last date the patient is known to be alive. OS will be evaluated by the Kaplan-Meier method and a 2-sided 95% CI will be provided for the median OS.

Time to progression (TTP) for responders only is measured from the time measurement criteria are first met for CR/PR (whichever is first recorded) until the first date that the criteria for PD are met, or death. TTP will be

estimated with the Kaplan-Meier method; a 90% CI will be provided for the median TTP. Patients who do not relapse are censored at the day of their last objective tumor assessment. The freedom from metastasis rate is defined below and will be calculated based on an intention to treat principle. Determination of the anatomic site of first failure for patients with PD will be recorded and analyzed. Duration of response is also defined below.

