15.4 Analysis of Safety Data

Safety analyses will be performed on all patients who receive any dose of study medication. Adverse events that occur more than 30 days after the administration of the last dose of treatment will not be included.

The safety and tolerability of study drug is determined by reported AEs, physical examinations, laboratory tests, and ECGs. All patients will be assessed regularly for potential occurrence of AEs from the time that treatment starts until 60 days after the last dose of study therapy. AEs will be summarized with the incidence and percentage of patients with at least one occurrence of a preferred term (according to the most severe NCI-CTCAE Version 4.0 grade) will be included. The number of AEs reported will also be summarized. Causality (relationship to study drug) will be summarized separately. Duration of AE will be determined and included in listings along with action taken and outcome. Laboratory AEs will be monitored from the time that treatment starts until 30 days after the last dose of study therapy. Laboratory results will be classified according to NCI-CTCAE, Version 4.0. Incidence of laboratory abnormalities will be summarized; laboratory results not corresponding to an NCI-CTCAE Version 4.0 term will not be graded. Laboratory toxicity shifts from baseline to worst grade will also be provided. The results from physical examination and vital sign measurement will be tabulated. Descriptive statistics will be provided as appropriate.

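### Toxicity is one of two aims, yet the protocol names no treatment-related or non-relapse death outcome, gives no interval for any toxicity rate, and states no event count that pauses accrual

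*Combined protocol and SAP*

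**What the plan says.** The second of the two aims (Section 3.2) is "To evaluate the toxicities associated with undergoing high dose conditioning" with the three-drug regimen and autologous rescue. Section 15.1 says that "a sample size of 10 patients was chosen based on availability", so no rate, precision or safety target lies behind the number.

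Death enters the plan in these places:

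- Section 12.2 lists "Results in death" as one criterion for a serious adverse event.
- Section 15.2 makes "death as a result of any cause" an event in PFS, the primary endpoint, alongside progression.
- Section 15.3 defines OS by death from any cause. Time to progression (15.3) and duration of response (15.5) also count death without separating its cause.

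For safety, Section 15.4 says "AEs will be summarized with the incidence and percentage of patients with at least one occurrence of a preferred term", by worst grade. Causality is tabulated separately, and listings give action taken and outcome. No interval is specified. Section 15.3 does specify exact 95% bounds for the response rate.

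Section 15.4 leaves out of the safety analysis events that start beyond 30 days from the last dose. The same section has patients assessed for adverse events to 60 days, and Section 12.6 collects serious events to 60 days.

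On oversight, Section 13 says "The Data and Safety Monitoring Committee will review all serious adverse events and toxicity reports as well as annual reviews". It also binds the study to the cancer center's own monitoring plan and has the investigator monitor continuously. Section 12.6 sends serious events to the IRB within 5 working days. The discontinuation criteria in Section 5.5.3 act on individual subjects, not on the study.

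**The concern.** For a high-dose regimen with stem cell rescue, the safety result a reader most needs is how many patients died of the treatment rather than of the cancer. Under this plan that number has to be pieced together from listings. In the primary endpoint a toxic death and a progression count alike.

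Section 15.4 says that tolerability will be judged from reported adverse events, laboratory tests and examinations. With ten patients a bare percentage is weak support for such a judgement, and a zero is the easiest result to over-read. The 30-day cut makes this worse, because a zero in the safety tables need not mean that no treatment-related death occurred.

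On conduct, review by judgement has no stated chance of acting at any given death rate. Without a written count, neither the committee nor a later reader can say what pattern of deaths would have prompted a pause.

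**Working it through.** **Inputs.** From the documents: n = 10 (Sections 5.2 and 15.1); exact 95% two-sided bounds, the plan's own convention for response (15.3); last chemotherapy on Day -2 (treatment table in 5.5.4); 30-day and 60-day windows (15.4, 12.6); AE assessment and imaging at Day 100, with no tumour imaging scheduled between baseline and Day 100 (Section 8). Assumed: the true rate of treatment-related death. The documents give none, so 5% to 50% is shown. The sample size has no formula behind it, so there is no planned figure to reproduce.

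**Windows.** If the last dose is the Day -2 chemotherapy, 30 days runs to -2 + 30 = Day +28 and 60 days to -2 + 60 = Day +58. A toxic death between those days would be collected as a serious event, left out of the safety analysis, and counted only as an undifferentiated event in PFS and OS.

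**Interval for a death rate.** For 0 of n, the exact two-sided 95% upper limit is 1 - 0.025^(1/n). With n = 10 this is 1 - 0.025^0.1 = 30.8%. The Clopper-Pearson interval for 1/10 is 0.3% to 44.5%, and for 2/10 it is 2.5% to 55.6%. The one-sided 95% upper limit for 0/10 is 1 - 0.05^0.1 = 25.9%.

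**How often zero is seen.** (1 - p)^10 is given in the last column of the table.

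**An illustrative pause count.** Suppose that accrual pauses at 2 deaths in the first 5 patients or 3 at any time. No pause occurs if there are 0 deaths in the first five and at most 2 in the next five, or 1 in the first five and at most 1 in the next five. At p = 0.30:

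P(no pause) = 0.16807 × 0.83692 + 0.36015 × 0.52822 = 0.1407 + 0.1902 = 0.331, so P(pause) = 0.669.

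Mean treated is the sum, over m = 0 to 9, of the probability that the count has not been reached after m patients. It takes each outcome as known before the next entry and every pause as final.

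| Assumed true rate | P(pause) | Mean treated | P(0 deaths in 10) |
|---|---|---|---|
| 5% | 2.8% | 9.86 | 59.9% |
| 10% | 11.3% | 9.47 | 34.9% |
| 20% | 38.9% | 8.22 | 10.7% |
| 30% | 66.9% | 6.73 | 2.8% |
| 50% | 95.5% | 4.26 | 0.1% |

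**Sensitivity of the illustration.**

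- If two more patients are treated before the deciding death is known, mean treated rises from 6.7 to 7.9 at 30%, and from 4.3 to 6.1 at 50%.
- Expected deaths are the rate times the mean treated. At 30% that is 0.30 × 6.73 = 2.0 without overlap and 0.30 × 7.9 = 2.4 with it, against 0.30 × 10 = 3 if all ten are treated.
- A pause reached only at patient 10 spares nobody. At 30% the chance of pausing earlier replaces the second five patients by four: 1 - (0.16807 × 0.9163 + 0.36015 × 0.6517) = 1 - 0.389 = 61%.

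**The case against.** The strongest case on the other side is that oversight exists. Every death is a serious event, the committee reviews all of them, the IRB hears within 5 working days, and the investigator monitors continuously. The institutional plan may contain a stopping criterion that the public documents do not show. All of this stands. A reader might infer that nothing prevents all ten patients being treated under a lethal regimen. The documents do not support that; they support only that this protocol states no boundary.

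A reader might also infer that toxic deaths go unrecorded. They do not. Section 15.4 gives worst grade, causality and outcome, so in ten patients a death inside the window should be traceable. What is missing is a defined rate with an interval, and coverage of deaths after the 30-day cut.

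Death rates of 30% to 50% have no source in the documents. Section 2 cites a six-patient series with manageable toxicity, in which the three deaths were from disease, and a second report of acceptable toxicity. At 20% the illustrative count pauses only 39% of the time. Its apparent savings also assume that every pause is permanent and that entries do not overlap. The documents give no accrual rate, so the second is an assumption. These figures should be read as best-case.

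Finally, this is a pilot with no declared tolerability threshold. That lowers the stakes but does not remove the case for an interval, since the plan already gives one for response in the same patients.

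**Conclusion.** The point holds in this limited form. The protocol has a toxicity aim but no treatment-related or non-relapse death outcome, no interval for any toxicity rate, and no study-level event count tied to accrual. Its 30-day and 60-day windows conflict in a way that could leave a toxic death out of the safety tables.

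The firmest figures are the intervals: zero deaths in ten is compatible, at the 95% level, with a true rate of up to 30.8%, and one death with up to 44.5%. They assume that all ten patients are dosed and that each one's status is known. The Day +28 figure assumes that the last dose means the Day -2 chemotherapy. The pause probabilities rest on assumed death rates and on one example count, and they show what a stated rule can be made to report, not what this trial would experience.

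This is a recommended improvement to reporting and monitoring. It does not show that the regimen is unsafe or that oversight is absent.

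**What to change.** 1. **Section 15.4, outcome.** Report death without documented progression by Day 100 as a named outcome, with an exact 95% CI, in all patients who receive any dose. Day 100 is already a scheduled visit. List the attributed cause of each such death, because with no imaging scheduled between baseline and Day 100 an early death from undetected progression could be counted as non-relapse. List PFS events by type; with ten patients a listing is enough.
2. **Section 15.4, windows.** Reconcile the 30-day analysis cut with the 60-day assessment in the same section and the 60-day collection in Section 12.6, and define the last dose.
3. **Section 15.4, intervals.** Give exact 95% CIs for the main toxicity rates.
4. **Section 13.** If the institutional plan has a stopping criterion, cite it. If not, have the committee pre-state a count of the same deaths as in item 1 that pauses accrual for its review. Print the operating characteristics over a range of assumed rates, with and without overlapping entries. The committee sets the acceptable rate and the count.

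The cost is about a paragraph in each of Sections 13 and 15.4, with no added patients or visits. The downside is an unnecessary pause: with the illustrative count, about 3% at a true rate of 5% and 11% at 10%.
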